5.2 Prohibited treatment

Use of the treatments displayed in [Table 5-1](#) is NOT allowed after the indicated period.

Table 5-1 Prohibited medication

Medication	Prohibited period	Action to be taken
Drugs that are known to strongly inhibit or induce the metabolizing enzymes CYP3A4/5, as they may alter the PK of LML134.	From at least 5 half-lives before first dosing through end of study	Do not enroll subject or initiate treatment. Discontinue study treatment during treatment periods.
Drugs or other non-pharmacological interventions that might affect circadian rhythm (e.g. melatonin, light therapy).	From start of screening through end of study.	Do not enroll subject or initiate treatment. Discontinue study treatment during treatment periods.
Modafinil and hypnotics	From at least 5-times the half-life of the drug prior to the start of screening through end of study.	Do not enroll subject or initiate treatment, unless it is safe to discontinue modafinil and hypnotics and the subject agrees to discontinue use of modafinil and hypnotics. Should the need arise for a subject to take modafinil or hypnotics during the study, the study drug should be discontinued.
All CNS-active medication including OTC cough suppressant (except modafinil and hypnotics)	From start of screening through end of study.	Do not enroll subject or initiate treatment. Should the need arise for a subject to take CNS active medication during the study, the study drug should be discontinued.
Antihistamines, in particular, first generation (i.e. brain penetrant, sedative) antihistamines (chlorpheniramine, diphenhydramine, promethazine, and hydroxyzine)	From at least 5-times the half-life of the drug prior to the start of screening through end of study.	Do not enroll subject or initiate treatment, unless it is safe to discontinue antihistamines and the subject agrees to discontinue use of antihistamines. Should the need arise for a subject to take antihistamines during the study, the study drug should be discontinued.

Medication	Prohibited period	Action to be taken
Any other drug, herbal or food supplement that might induce sleepiness/somnolence or sedation as a known and common AE (>1%) according to the label of the drug and medical history of the subject indicates that the excessive sleepiness might be related to use of these drugs or food supplements. Examples include antiemetics, alpha-adrenergic blocking agents, some beta adrenergic blocking agents, muscle relaxants and other drugs.	From start of screening through end of study.	Do not enroll subject or initiate treatment. Should the need arise for a subject to take such medication during the study, the study drug should be discontinued.
Combination drug treatments that contain caffeine.	From at least 12 hours before dosing to end of assessments during the treatment period	Discontinue study treatment and remove subject from efficacy analysis.

5.3 Dietary restrictions and smoking

- No alcohol for 12 hours before each dosing. Consumption of alcohol is not permitted at any time while the subjects are domiciled. During the out-patient phase of the study consumption of alcohol will be restricted to no more than one drink per day for women and no more than two drinks per day for men. A standard drink (in the United States) is equal to 14.0 grams (0.6 ounces) of pure alcohol. Generally, this amount of pure alcohol is found in
 - 12 fluid ounces of regular beer (5% alcohol content)
 - 5 fluid ounces of wine (12% alcohol content)
 - 1.5 fluid ounces or a “shot” of 80-proof (40% alcohol content) distilled spirits or liquor (e.g., gin, rum, vodka, whiskey)
- No cannabis use for 4 weeks before first dosing until after Study Completion evaluation.
- Smokers should not smoke more than 10 cigarettes per day during the entire study period. Consumption of nicotine containing products is also restricted to equivalent amount (corresponding to 10 cigarettes) during the entire study period. Smoking is completely prohibited during the treatment period each night from about 2 hours before dosing until completion of all efficacy assessments.
- Intake of methylxanthine (e.g. caffeine, theophylline, theobromine) containing food or beverages must be discontinued 12 hours before dosing. Consumption of such foods and beverages (i.e., coffee, tea, soda, chocolate) is not permitted at any time while the subjects are domiciled. During the out-patient phase of the study caffeine consumption will be restricted to no more than 850 mg of caffeine per day.
- No grapefruit or grapefruit juice is to be consumed for 14 days prior to dosing until 7 days following the last dose.

Subjects should take medication when administered by site staff. Study medication should be administered with a glass of water. Subjects should not chew the medication, but swallow it whole.

Meals and snacks will be served at appropriate times according to the subjects' sleep/wake schedules and so as not to interfere with the [Assessment schedule](#). Subjects will follow a standard weight maintaining diet while domiciled.

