On Night 1, safety assessments, Corporate Confidential Information will be performed after daytime sleep but before dosing. If timing of the daytime sleep period would not allow completion of all necessary assessments before dosing, the physical and neurological exams, CSSR-S and alcohol/drug/cotinine screen can be completed before the subject goes to sleep in the morning. The subjects will receive the first dose of assigned drug at approximately 22:00, and will then perform a series of assessments repeated at regular intervals throughout the night. Wakefulness will be assessed using Corporate Confidential Information the MSLT at approximately 1:30, 3:30, 5:30 and 7:30.

Subjects are not allowed to nap during the assessment nights outside the MSLT exams. They will be continuously supervised by site personnel to make sure they stay awake during the test nights.

Subjects will remain in the clinic for recovery sleep during Day 2 starting in the morning at approximately 10:00, and will undergo PSG to assess daytime sleep. Total time spent in bed on Day 2 should be approximately 8 hours. Corporate Confidential Information

Subjects will also be requested to fill out a sleep diary upon waking on the days specified in the [Assessment schedule](#).

Safety assessments, Corporate Confidential Information will be performed again after daytime sleep but before dosing on Day 2, similarly to Day 1. Subjects will receive the second dose of assigned drug at approximately 22:00 on Night 2. Night 2 assessments will be identical to those completed on Night 1 at approximately the same clock time. Corporate Confidential Information

Once all assessments on the morning of Day 3 have been completed, subjects can either remain in the clinic for Day 3 recovery sleep, or will be provided with safe transportation home for recovery sleep, if all safety assessments have been completed with satisfactory results.

Subjects will return to the clinical site for a follow-up visit for safety purposes 7 to 14 days after completion of treatment in both periods. The safety follow-up visit after the first period can also serve as baseline visit for the second period, if Treatment period 2 Day 1 occurs within 7 days of the visit. Sparse PK sampling will be done over the two day study period as indicated in the [Assessment schedule](#) to obtain an optimal exposure estimation with the help of the established Pop-PK model.

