- Male sterilization (at least 6 m prior to screening). The vasectomized male partner should be the sole partner for that subject
- Use of oral, injected or implanted hormonal methods of contraception or placement of an intrauterine device (IUD) or intrauterine system (IUS) or other forms of hormonal contraception that have comparable efficacy (failure rate <1%), for example hormone vaginal ring or transdermal hormone contraception

In case of use of oral hormonal contraception or other forms of hormonal contraception (e.g. vaginal ring or transdermal patch) women should have been stable on the same pill/method for a minimum of 3 months before starting study treatment. In case of use of an IUD or IUS, the device or system should have been placed and well tolerated by the patient for a minimum of 3 months before starting the study treatment.

Women are considered post-menopausal and not of child bearing potential if they have had 12 months of natural (spontaneous) amenorrhea with an appropriate clinical profile (e.g. age appropriate, history of vasomotor symptoms) or have had surgical bilateral oophorectomy (with or without hysterectomy), total hysterectomy or tubal ligation at least six weeks ago. In the case of oophorectomy alone, only when the reproductive status of the woman has been confirmed by follow up hormone level assessment is she considered not of child bearing potential

9. Sexually active males unwilling to use a condom during intercourse while taking investigational drug and for 3 days after stopping investigational drug in both study periods. A condom is required for all sexually active male participants to prevent them from fathering a child AND to prevent delivery of the investigational drug via seminal fluid to their partner.
10. Heavy smokers who smoke more than 10 cigarettes a day and occasional or light smokers (not more than 10 cigarettes per day) who are not willing to, or in their own or the investigators opinion are not able to refrain from tobacco/nicotine use for at least 12 hours without nicotine craving or other withdrawal symptoms (e.g. anxiety, irritability, restlessness, sweating, headache, etc.).

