- ¹³ Screening assessments will occur over multiple days. The daytime sleep PSG and nighttime MSLT will be performed in the sleep lab on consecutive days that follow at least 3 consecutive nights following a shift work schedule.
- ¹⁴ If a subject spends an additional supervised night in the sleep lab to complete their third consecutive awake night this must be documented in the sites source records. Records should include the date of the stay and the schedule they followed during their stay.
- ¹⁵ EOS/ET assessments should not be repeated if performed during the follow-up visit at the end of the Treatment Period. If subjects terminate early the EOS assessments should be completed prior to the patient leaving the sleep laboratory and the patient should return for the follow-up visit.
- ¹⁶ The Follow-up visit in Treatment Period 1 can also serve as the Baseline 2 visit if Treatment Period 2 Day 1 will begin within 7 days after the visit
- ¹⁷ Follow-up assessments should be completed for any patient who receives test drug 7 to 14 days after they discontinue study treatment in each treatment period.
- ¹⁸ Safety follow-up phone call to be performed 30 days after last visit for enrolled subjects.
- ¹⁹ Up to 5 weeks wash out is allowed between the last dose in Treatment period 1 and the first dose of period 2 to allow for scheduling flexibility. Timing of the second baseline visits should be adjusted accordingly.
- ²⁰ The assessments should be performed as close as possible to the dosing time. If timing of the daytime sleep period would not allow completion of all necessary assessments before dosing, the physical and neurological exams, CSSR-S and alcohol/drug/cotinine screen can be completed before the subject goes to sleep in the

Corporate Confidential Information

- ²² Dosing should be performed at approximately 22:00.
- ²³ 9.5h assessments are detailed in the details for night time assessments table
- ²⁴ Safety assessments may commence after completion of efficacy assessments.
- ²⁵ Safety assessments should be done prior to discharge. These assessments can be completed after the efficacy assessments Corporate Confidential are completed, if the patients decide to leave the site in the morning. If the subject stays in the clinic to sleep these assessments can be done after the recovery sleep is completed
- ²⁶ Any occurrence of protocol exclusion criteria #6, #13, #19, #20, at the second Baseline visit would result in discontinuation

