11.4.2 Statistical model, hypothesis, and method of analysis

Nicotine is a powerful substance to stimulate wakefulness and attention. At same time screening MSLT reflects the stage of severity of shift work disorder patients. Therefore both smoking status (/nicotine intake) and MSLT at screening will be considered as covariates in the model.

For statistical analysis purposes; subjects under full analysis set with all available MSLT information from both the periods will be included in the analysis.

Mean sleep latency score data will be analyzed using a mixed effect ANOVA model with treatment smoking status at screening, screening MSLT, treatment interaction with screening MSLT and smoking status and period as fixed effects and subject as a random effect. Least square estimates for each treatment and treatment difference (LML134 vs placebo) along with 95% confidence interval will be reported. In studies with short treatment duration in SWD patients or healthy shift workers the usual approach is to compare post-dose conditions and not change from baseline. The reason for this approach is the high variability in MSLT (average of at least three tests is needed as baseline) and that baseline and post-dose MSLT results need to be time matched, as MSLT results depend on circadian rhythm.

The following assessments will be performed to judge efficacy of LML134:

a. Statistical significance: One sided (superiority) p-value of LML134 vs placebo from above fitted ANOVA model will be reported.

A p-value <0.1 will be considered as a positive sign for statistical significance.

b. Estimate of treatment difference (LML134 vs Placebo) will be reported.

An estimate of treatment difference > 1 minute would be considered as significant.

In addition from the above model, effect of LML over placebo in each subgroup (smoking status and MSLT (<6 and ≥ 6)) will be estimated through 95% CI of interaction effects.

Same analysis will be performed at interim.

Graphical display:

Subjects under safety analysis set will be used for reporting. For a thorough investigation of sleep latency time profiles, data from LML134 and placebo will be superimposed using suitable graphical tools like boxplot or arithmetic mean (SD) statistics.

Descriptive summary:

Subjects under safety analysis set will be used for reporting. Sleep latency data will be summarized by treatment and time point. Summary statistics like N, mean, SD, CV, and range will be reported.

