6.1.3 Statistical model, assumptions and hypotheses

MSLT from both periods will be included in the analysis.

Corporate Confidential Information

Due to high variability and time difference between screening MSLT and post treatment records, screening MSLT will not be used as a covariate for modelling. Total sleep time from sleep diary data during baseline will be used as baseline covariate. Therefore both smoking status (nicotine intake) and total sleep time at baseline will be considered as covariates in the model.

The primary variable, mean MSLT of a subject within a period, will be analyzed using a mixed effect analysis of variance model. This model will have the mean MSLT as the dependent variable; treatment, actual treatment sequence, smoking status at screening, total sleep time at baseline, treatment interaction with total sleep time at baseline and smoking status and period as fixed effects and a subject level random intercept. Primary analysis will be assessed over full analysis set.

Least square estimates for each treatment (LML134 and placebo) and treatment difference (LML134 vs placebo) along with 95% confidence interval will be reported.

The following assessments will be performed to judge efficacy of LML134:

1. Statistical significance: One sided (superiority) p-value of LML134 vs placebo from above fitted ANOVA model will be reported.

A p-value < 0.1 will be considered as a positive sign for statistical significance.

2. Estimate of treatment difference (LML134 vs Placebo) will be reported.
An estimate of treatment difference > 1 minute would be considered as significant.

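### The test-night ban in Protocol 5.3 names only smoking, so other nicotine products stay permitted up to a cap while the primary endpoint is measured

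*Protocol*

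**What the plan says.** Protocol 5.3 deals with smoking in three consecutive statements. Smokers are limited to 10 cigarettes a day throughout the study. Other products follow the same limit: "Consumption of nicotine containing products is also restricted to equivalent amount (corresponding to 10 cigarettes) during the entire study period". The test nights then get a stricter rule: "Smoking is completely prohibited during the treatment period each night from about 2 hours before dosing until completion of all efficacy assessments".

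Three other places bear on the scope of that rule.

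- **Protocol 4.2, Exclusion 10** removes heavy smokers. It also removes light or occasional smokers who are unwilling or "not able to refrain from tobacco/nicotine use for at least 12 hours without nicotine craving or other withdrawal symptoms".
- **Protocol 11.4.2** explains why smoking is in the model: "Nicotine is a powerful substance to stimulate wakefulness and attention".
- **SAP 6.1.3** keeps the adjustment: "Therefore both smoking status (nicotine intake) and total sleep time at baseline will be considered as covariates in the model". The model term is smoking status at screening, with a treatment interaction.

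On timing, the assessment schedule (Protocol 8.1) states "Dosing should be performed at approximately 22:00", and Protocol 3.1 places "the MSLT at approximately 1:30, 3:30, 5:30 and 7:30" on each treatment night.

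**The concern.** The stated worry is nicotine, but the conduct rule addresses one way of taking it. Section 5.3 has just named nicotine-containing products as a separate category, so their absence from the next sentence reads as a real difference in scope. Methylxanthines are handled differently in the same section: they are stopped by substance from 12 hours before dosing and not permitted at all while subjects are domiciled.

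What is at stake is the within-subject contrast. A subject who uses nicotine in one period and not in the other, or more in one than in the other, carries that difference straight into the LML134-minus-placebo comparison. Use unrelated to treatment adds noise. Use that rises on the sleepier nights, which would be the placebo nights if the drug works, shrinks the estimated difference.

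**Working it through.** **Step 1. Compare the scope of each rule.**

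| Place | What it covers | When |
|---|---|---|
| Protocol 5.3, cap | Cigarettes and, by equivalence, other nicotine products | Entire study |
| Protocol 5.3, complete ban | Smoking only | About 2 h before dosing to end of efficacy tests |
| Protocol 4.2, Exclusion 10 | Willingness and ability to do without tobacco/nicotine | At least 12 h |
| Protocol 11.4.2, rationale | Nicotine | Not time-bound |

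No other visible section bans nicotine products by name on the test nights.

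**Step 2. Length of the window.** Dosing at about 22:00 minus 2 h gives about 20:00. From 20:00 to the start of the last nap at about 7:30 is 4 + 7.5 = 11.5 h, so about 12 h once that nap is finished. This is close to the 12 h in Exclusion 10, although the protocol does not itself link the two.

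**Step 3. Do other safeguards close the gap?**

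- *Covariate.* Smoking status at screening has one value per subject. Its main effect is the same in both periods and drops out of the within-subject contrast. The treatment interaction could show a smaller difference in smokers, but could not say whether the drug or test-night nicotine caused it.
- *Cotinine.* The schedule places it at screening, both baselines and before dosing on Day 1 of each period. All of these precede the test nights.
- *Table 5-1.* The row on CNS-active medication does not name nicotine. If it did cover nicotine, it would forbid from screening onwards what 5.3 permits up to a cap.

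**Step 4. Reproduce the plan's own operating characteristic.** Inputs from Protocol 11.7: 36 evaluable subjects, SD 4 min, true effect 2 min, p < 0.1 (one-sided, 11.4.2) and an estimate above 1 min.

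- SE = 4 × √(2/36) = 0.943
- Significance needs an estimate above 1.2816 × 0.943 = 1.208. This exceeds 1, so it is the binding criterion.
- P(both met) = Φ((2 − 1.208)/0.943) = Φ(0.840) = 79.9%, against 80.0% in Table 11-1. The other rows of that column also reproduce.

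**Step 5. Use unrelated to treatment (assumed inputs).** Suppose a share f of subjects use nicotine in a random half of periods and it adds m minutes to the period mean. The added variance per period is f × m² × 0.25, and the steps above are repeated with SD = √(16 + f·m²/4).

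| f | m (min) | SD | P(both met) |
|---|---|---|---|
| 10% | 1 | 4.003 | 79.9% |
| 20% | 2 | 4.025 | 79.6% |
| 30% | 4 | 4.147 | 77.8% |

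**Step 6. Use on placebo nights only (assumed worst case).** If a share f uses nicotine only on placebo nights and it adds d minutes, the expected difference falls by f × d.

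- f = 10%, d = 1: 0.1 min. Effective difference 1.9; Φ((1.9 − 1.208)/0.943) = 76.8%.
- f = 20%, d = 3: 0.6 min. Effective difference 1.4; Φ((1.4 − 1.208)/0.943) = 58.1%.

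Neither f, m nor d comes from the documents. Steps 5 and 6 show direction and range; they do not forecast a result.

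**The case against.** The strongest reply is that this is one loosely worded sentence in a tightly controlled setting. Subjects are domiciled and continuously supervised on the test nights, light smokers have been selected for coping 12 hours without nicotine, and treatment is blinded. Steady use in both periods would largely cancel. A site might treat e-cigarettes as smoking, or nicotine replacement as CNS-active medication. The Site Operations Manual, which is not available here, may say more about smokers and about MSLT procedure. All of this stands as a reason to expect a small effect. It does not supply the missing restriction: the supervision described in Protocol 3.1 is for keeping subjects awake, and ability to abstain is not an instruction to abstain.

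A reader might go further in four ways that the documents do not support.

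- *That sites must allow nicotine use.* A missing ban creates no duty to permit.
- *That Exclusion 10 requires abstinence, so the two rules contradict each other outright.* It is an entry criterion on willingness and ability. A wider entry criterion sits awkwardly with a narrower conduct rule, but both can be followed.
- *That heavy users of non-cigarette nicotine are modelled as non-smokers.* Both documents gloss the covariate as nicotine intake, and such users are also bound by the cap in 5.3.
- *That smoking is allowed on the screening MSLT night.* The ban's wording is limited to the treatment period, but Protocol 8.5.1 says that screening uses the same approach as the efficacy test. The screening position is unstated.

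**Conclusion.** The point holds as a gap in scope. As written, capped non-smoked nicotine remains permitted during the naps that form the primary endpoint, although the protocol gives nicotine's effect on wakefulness as its reason for adjusting the analysis. The planned adjustment cannot remove use that differs between periods.

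Severity is low to moderate, and the true size is unknown. If use is unrelated to treatment, the loss is about two percentage points at most over the range tried (79.9% to 77.8%). If use concentrates on placebo nights, the bias is towards no effect, by 0.1 to 0.6 min under the assumed inputs. The upper end should not be read as an expected value against the 1-minute criterion, because it puts all use on placebo nights in a blinded crossover. All these figures use the planned 36 evaluable subjects. SAP 1.4 reports termination after 18 completers, where one subject is 1/18 = 5.6% of the data.

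**What to change.** Reconcile Protocol 5.3, Exclusion 10 and 11.4.2 so that the substance and the window agree:

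1. In 5.3, make the existing test-night restriction cover smoking and any nicotine-containing product, over the same window.
2. State that the same restriction applies on the screening MSLT night, in line with the common approach in 8.5.1.
3. Record any nicotine use on test nights, by period, and list it with the primary endpoint data.

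Exclusion 10 needs no rewriting. The cost is two wording changes and one recorded item, and it asks of light smokers only what Exclusion 10 already screens them for. Because the study stopped early, a conduct change cannot reach the data already collected. For those, any test-night nicotine use found in source records should be listed and the gap reported as a limitation, with the wording corrected before the protocol text is reused.
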